9.4.11 Functional Assessment of Chronic Illness Therapy (FACIT) – Fatigue Scale

Fatigue is one of the most frequent complaints of individuals with RA and is strongly associated with loss of independence, decreased physical activity and functional decline. One validated tool to measure fatigue is the FACIT Fatigue scale v4. The FACIT Fatigue Scale is a short, 13-item, easy to administer tool that measures an individual's level of fatigue during their usual daily activities over the past week. The level of fatigue is measured on a four point Likert scale (4 = not at all fatigued to 0 = very much fatigued). The Fatigue scale is ranged from 0 to 52 and the higher the score, the better the quality of life.

Item score for each item is calculated by either subtracting from 4 or adding 0 depending on whether it is a reversal item or not. FACIT Fatigue Scale is then calculated by adding up all item scores, multiplying by 13 and dividing by the number of items answered. It is essentially a prorated subscale if there are missing values for some items. If less than or equal to 50% of the items are answered (e.g., 6 out of 13), the proration is not acceptable and the scale will not be computed. Detailed calculation and missing value handling are documented in [Appendix A](#).

9.4.12 Work Instability Scale for RA (RA-WIS)

The 23-item RA-WIS is a simple validated tool to evaluate Work Instability (the consequence of a mis-match between an individual's functional ability and their work tasks). It can be self-administered by the patients. To calculate the RA-WIS score,

one can simply add up the number of "true" responses. The RA-WIS can be scored in three bands indicating low (< 10), medium (10 – 17), and high (> 17) risk of work disability. The state of 'mismatch' between functional incapacity and work demands can threaten continuing employment if not resolved.

9.4.13 EuroQoL-5D (EQ-5D)

EQ-5D is a standardized measure of health status developed by the EuroQol Group in order to provide a simple, generic measure of health for clinical and economic appraisal. The EQ-5D consists of 2 pages. The first page measures 5 dimensions of the health status (mobility, self-care, usual activities, pain/discomfort, and anxiety/depression) with 5 levels per dimension (no problems, slight problems, moderate problems, severe problems, and extreme problems corresponding to Level 1 to Level 5 respectively). The second page is an EQ Visual Analogue Scale (EQ VAS). EQ-5D health states, defined by the EQ-5D-5L descriptive system on the first page, may be converted into a single index value. The change from baseline of the index value and EQ VAS will be analyzed and reported. The details of conversion and missing data handling can be found in EQ-5D manual ([Appendix B](#)). UK scoring algorithm will be used.

10.0 Safety Analysis

10.1 General Considerations

Safety analyses will include reporting of adverse events, laboratory, and vital signs measurements in open-label treatment period only. Safety analyses will be carried out using the Open-Label Treated Population, which includes all subjects who received at least one dose of open-label study medication.

Long-term safety analyses include reporting of AE rate adjusted by cumulative exposure, mean change from baseline in laboratory parameters and vital sign variables, and frequency of potentially clinically significant laboratory and vital signs values.

The treatment-emergent adverse event (TEAE) rate per 100 patient-years of exposure will be presented by the exposure groups defined in Section 8.1, namely

1. Upadacitinib 6 mg BID/15 mg QD
2. Upadacitinib 12 mg BID/30 mg QD
3. Upadacitinib 6 mg BID/15 mg QD post down titration
4. Any upadacitinib

Listing of subjects with TEAEs by SOC and PT will be provided. Frequency tables and listings of subjects meeting criteria for potentially clinically significant vital sign values and for potentially clinically significant laboratory values will be provided by the exposure groups defined in Section 8.1.

Mean changes from baseline in all continuous laboratory parameters and vital signs variables at each visit will be summarized by the treatment group sequences defined in Section 9.1, namely

1. Upadacitinib never titrated (6 mg BID/15 mg QD),
2. Upadacitinib titrated up and not down (6 mg BID/15 mg QD to 12 mg BID/30 mg QD), and
3. Upadacitinib titrated up and down (6 mg BID/15 mg QD to 12 mg BID/30 mg QD and then back down to 6 mg BID/15 mg QD).

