8.0 Study Drug Exposure and Compliance

8.1 Study Drug Exposure

The duration of exposure to study drug in M13-538 will be summarized for the Open-Label Treated Population by the following groups:

1. Upadacitinib 6 mg BID/15 mg QD

This includes upadacitinib 6 mg BID or 15 mg QD exposure from subjects who never titrated, as well as the upadacitinib 6 mg BID or 15 mg QD exposure prior to dose titration for subjects who titrated (censored at the time of up titration to 12 mg BID/30 mg QD).

2. Upadacitinib 12 mg BID/30 mg QD

This includes upadacitinib 12 mg BID or 30 mg QD exposure for subjects who titrated up (censored at the time of down titration to 6 mg BID/15 mg QD for subjects who titrated up and back down).

3. Upadacitinib 6 mg BID/15 mg QD post down titration

This includes upadacitinib 6 mg BID/15 mg QD exposure after down titration for subjects who titrated up and back down.

4. Any upadacitinib

This includes any upadacitinib exposure in Study M13-538.

The first three exposure groups are mutually exclusive in terms of exposure, and the three groups combined is represented by the fourth group.

The duration of exposure to study drug will be summarized for each exposure group as specified above, with the number of subjects, mean, standard deviation, median, minimum and maximum values. In addition, the number and percentage of subjects exposed to study drug will be summarized for the following cumulative duration intervals.

Open-label exposure:

- ≥ 6 months
- ≥ 12 months
- ≥ 18 months
- ≥ 2 years
- ≥ 2.5 years
- ≥ 3 years
- ≥ 4 years
- ≥ 5 years

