10.3.5 Analyses for Liver Elevations

According to FDA's Guidance for Industry "Drug-Induced Liver Injury: Premarketing clinical evaluation (July 2009), when aminotransferase (AT) abnormalities indicating hepatocellular injury are accompanied by evidence of impaired hepatic function (bilirubin elevation $> 2 \times \text{ULN}$), in the absence of evidence of biliary obstruction (i.e., significant elevation of ALP) or some other explanation of the injury (e.g., viral hepatitis, alcohol hepatitis), the combined finding (i.e., Hy's Law cases) represents a signal of a potential for the drug to cause severe DILI.

For the purpose of assessing for potential Hy's law cases, the frequencies and percentages of subjects with post baseline liver specific function test values that meet the following criteria of potential clinical interest will be summarized by exposure group:

- $\text{ALT} \geq 3 \times \text{ULN}$
- $\text{ALT} \geq 5 \times \text{ULN}$
- $\text{ALT} \geq 10 \times \text{ULN}$

- ALT $\geq 20 \times$ ULN
- AST $\geq 3 \times$ ULN
- AST $\geq 5 \times$ ULN
- AST $\geq 10 \times$ ULN
- AST $\geq 20 \times$ ULN
- TBL $\geq 2 \times$ ULN
- Alkaline phosphatase $\geq 1.5 \times$ ULN
- ALT and/or AST $\geq 3 \times$ ULN and concurrent TBL $\geq 1.5 \times$ ULN
- ALT and/or AST $\geq 3 \times$ ULN and concurrent TBL $\geq 2 \times$ ULN

A listing of potentially clinically significant liver elevations based on criteria specified above will be provided. For each of these subjects, the whole course of the respective parameter will be listed.

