10.4.2 Analysis of Long-Term Vital Signs

Mean changes from Baseline to post-baseline visits will be summarized with the baseline mean, the visit mean, change from baseline mean, standard deviation, and median. The number and percentage of subjects meeting the criteria for potentially clinically significant vital sign values will be summarized.

A listing of all subjects with any vital sign values meeting the criteria for potentially clinically significant vital signs will be provided. For each of these subjects, the whole course of the respective parameter will be listed.

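### Liver-threshold and clinically significant vital-sign findings are tabulated by exposure group without person-time, so crude percentages may differ between groups at equal risk

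*SAP*

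**What the plan says.** SAP 10.1 plans "Frequency tables and listings of subjects meeting criteria for potentially clinically significant vital sign values". The same sentence extends this to laboratory findings: output "for potentially clinically significant laboratory values will be provided by the exposure groups defined in Section 8.1". SAP 10.3.5 covers ALT and AST multiples, bilirubin, alkaline phosphatase and the combined criteria used to screen for potential Hy's law cases. It asks for "the frequencies and percentages of subjects with post baseline liver specific function test values", with the grouping given as "criteria of potential clinical interest will be summarized by exposure group". SAP 10.4.2 says: "The number and percentage of subjects meeting the criteria for potentially clinically significant vital sign values will be summarized".

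SAP 8.1 defines the groups:
- Group 1 is lower-dose time, ended at up-titration.
- Group 2 is higher-dose time, ended at down-titration.
- Group 3 is lower-dose time after down-titration.
- Group 4 is any upadacitinib.

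It states: "The first three exposure groups are mutually exclusive in terms of exposure".

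For adverse events the SAP does allow for time: "Long-term safety analyses include reporting of AE rate adjusted by cumulative exposure". Sections 10.2.1, 10.2.2, 10.2.4 and 10.2.5 apply rates per 100 patient-years to the same groups. Section 10.2.1 also gives subject percentages, but places rates beside them.

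**The concern.** The groups divide each subject's treatment time, so time at risk differs by construction. Up-titration is possible from Week 6 (SAP 4.2). A subject up-titrated then and kept on the higher dose contributes about 6 weeks to group 1 and up to about 306 weeks to group 2. A subject never titrated can contribute about 312 weeks to group 1. Entry to group 3 needs an up-titration and a later down-titration, and one discretionary route into it opened only with Amendment 5.

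The percentage of subjects who ever meet a criterion rises with time and with the number of tests in the segment. Read across columns, these tables therefore mix risk with duration. Long-term safety is part of the primary objective (SAP 4.1), and these are among its main laboratory and vital-sign outputs.

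**Working it through.** The plan states no expected frequency or duration for these tables, so there is no figure of its own to reproduce.

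**Inputs from the documents**
- Earliest up-titration: Week 6 (SAP 4.2), 42 / 365.25 = 0.115 year.
- Treatment length: about 312 weeks (SAP 4.2), 312 × 7 / 365.25 = 5.98 years.
- Scheduled post-baseline visits in SAP Table 1: 27.
- Amendment 5 dated 09 November 2019 (Protocol 1.1); SAP version 3.0 dated 03 May 2021 (SAP 11.0). The interval is 541 days, 541 / 365.25 = 1.48 years.

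**Assumptions**
- Constant first-event rates of 1 to 10 per 100 patient-years, because the documents give none.
- The SAP date stands in for a data cut in the 1.48-year case. That case applies only to subjects entering group 3 through Amendment 5.

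**Crude percentage at equal risk:** 100 × [1 − exp(−λT)], with λ the yearly rate and T the years observed.

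At λ = 0.03:
- T = 0.5: 1 − exp(−0.015) = 1.5%
- T = 1: 1 − exp(−0.03) = 3.0%
- T = 4: 1 − exp(−0.12) = 11.3%

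From 0.5 to 4 years the percentage rises about 7.6-fold (11.31 / 1.49) with no change in risk.

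Across the assumed range:

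| Rate per 100 PY | 6 weeks | 1 year | 1.48 years | 3 years | 312 weeks | Ratio, 312 weeks to 1.48 years |
|---|---|---|---|---|---|---|
| 1 | 0.1% | 1.0% | 1.5% | 3.0% | 5.8% | 4.0 |
| 2 | 0.2% | 2.0% | 2.9% | 5.8% | 11.3% | 3.9 |
| 5 | 0.6% | 4.9% | 7.1% | 13.9% | 25.8% | 3.6 |
| 10 | 1.1% | 9.5% | 13.8% | 25.9% | 45.0% | 3.3 |

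**By number of tests:** with an assumed 0.5% chance at each visit, 1 − 0.995^n gives 0.5% for 1 visit, 3.0% for 6 and 12.7% for 27.

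**Incidence rate on the same data:** expected first events per subject are 1 − exp(−λT), and expected time at risk is [1 − exp(−λT)] / λ. Their ratio is λ for every T. In a simulation of 400,000 subjects per case at a true 2 per 100 patient-years, the rate was 2.01, 1.99, 2.02 and 2.01 for 1, 1.48, 3 and 5.98 years. The crude percentages were 1.99%, 2.90%, 5.88% and 11.34%.

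**The case against.** **No comparison is planned.** The objective is to describe long-term safety, not to compare doses, and the SAP plans no tests. The any-upadacitinib column is untouched by an argument about differences between groups. This stands, but the tables set the three dose segments side by side, and the SAP uses rates for adverse events laid out in the same way.

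**Other outputs help.** Exposure is summarised for the same groups (8.1), and patient-years accompany the adverse event rates (10.2.1). Anemia, neutropenia, lymphopenia, CPK elevation, hepatic disorder and renal dysfunction are reported per 100 patient-years (10.2.5). Listings show the full course for each flagged subject, so a potential Hy's law case can be examined individually. These help a reader but adjust none of the threshold tables. Protocol 6.3.1 makes laboratory and vital-sign changes adverse events only under stated conditions, and SAP Table 5 has no category for the blood pressure or weight criteria.

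**A rate has its own limits.** It is free of duration only if the hazard is roughly constant. If abnormalities cluster early, long follow-up dilutes it. A weight change of more than 7% from the RCT baseline builds up over time and fits that assumption poorly. Titration follows response or toxicity, and no rate removes that confounding. Subjects may already meet a criterion when they enter a later segment. All of this stands and shapes the fix.

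**Stronger readings go too far.** A reader might infer that longer-treated groups, or a particular dose, will look worse in this trial. The documents give no group durations, and group 1 pools subjects who leave at Week 6 with subjects treated for about 312 weeks. A reader might also take Grade 3 or 4 laboratory values to be planned as percentages. Section 10.1 says only that they appear in frequency tables, and 10.3.4 describes a listing.

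**Conclusion.** The point holds as a gap in presentation. Liver-threshold and vital-sign findings are explicitly planned as numbers and percentages of subjects, and laboratory values as frequency tables. None has a person-time denominator, although the time at risk in the exposure groups differs by construction. At equal risk the percentages may differ severalfold: 3.3 to 4.0 times between 312 weeks and 1.48 years at the assumed rates. These figures, like the 7.6-fold contrast between 0.5 and 4 years, rest on assumed rates and chosen durations. They do not estimate bias in this trial, where neither the size nor the disadvantaged group can be determined from the documents. The change should be made, because the plan already accepts the principle for adverse events and the cost is low.

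**What to change.** In SAP 10.1, 10.3.5 and 10.4.2, keep the counts and percentages and add two columns by exposure group: patient-years at risk, and the first-occurrence incidence rate per 100 patient-years. Time at risk runs from entry to the segment until first occurrence or end of exposure in that group. Count as at risk only subjects not already meeting the criterion on entering the segment. The rule is needed because baseline is the RCT baseline (SAP 5.2). In 10.3.4, say what the laboratory frequency tables contain and apply the same addition.

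Add a short note stating that:
- the rate, not the crude percentage, is the figure for any descriptive reading across groups;
- it assumes a roughly constant hazard, and is less apt for cumulative criteria such as the 7% weight change;
- it does not remove confounding from response- or toxicity-driven titration.

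The cost is modest programming and longer tables. Exposure by group is already derived for the adverse event rates; time to first occurrence and status at segment entry are new.

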## **5.0 Investigational Plan**

### **5.1 Overall Study Design and Plan: Description**

This is a Phase 2, multicenter, OLE study to assess the long-term safety, tolerability, and efficacy of upadacitinib in RA subjects who have completed Study M13-550 or Study M13-537 Phase 2 RCT with upadacitinib. This study is designed to enroll up to 500 subjects. Subjects will be treated for approximately 312 weeks.

Only those subjects who have met all of the specified inclusion criteria and none of the exclusion criteria will have an option to enter into the OLE study to receive upadacitinib, as long as the subject is willing and the Investigator believes that continuing therapy with upadacitinib is appropriate.

All eligible subjects will be assigned to upadacitinib 6 mg BID immediately after or up to 30 days following the Last Visit (Week 12) of Study M13-550 or Study M13-537 Phase 2 RCT.

Subjects who are unable to tolerate 6 mg BID will be discontinued from the study.

At Week 6, if a subject fails to achieve at least 20% improvement from RCT Baseline in both Tender Joint Count (TJC) and Swollen Joint Count (SJC), upadacitinib dose should be increased to 12 mg BID as long as the Investigator has no safety concerns. After 6 weeks of treatment with upadacitinib 12 mg BID, the improvement in TJC and SJC will be re-assessed at next scheduled visit (Week 12).

If the subject on 12 mg BID fails to achieve at least 20% improvement in both TJC and SJC from RCT Baseline the subject will be discontinued.

At Week 12, the same process will be followed. If a subject still on 6 mg BID fails to achieve at least 20% improvement from RCT Baseline in both TJC and SJC, upadacitinib dose should be increased to 12 mg BID. The improvement in both TJC and SJC will be re-assessed after 6 weeks of treatment with 12 mg BID at Week 18 (an optional study visit).

Subjects who fail to achieve at least 20% improvement from RCT Baseline in both TJC and SJC with 12 mg BID at Week 18 will be discontinued.

After Week 12, if a subject fails to show at least 20% improvement from RCT Baseline in both TJC and SJC at 2 consecutive scheduled study visits, the subject will be discontinued.

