Starting at Week 6 and during any scheduled or unscheduled visits thereafter, upadacitinib dose may be increased from 6 mg BID to 12 mg BID (or 30 mg QD from January 2017, see below) if a subject fails to achieve Low Disease Activity (LDA) status (defined by CDAI > 10) and has no safety concerns per Investigator's judgment.

At any visit, upadacitinib dose may be decreased back to 6 mg BID (or 15 mg QD from January 2017) per Investigator's judgment if there are safety and/or tolerability concerns, due to an adverse event or reaching one of the protocol specific toxicity management thresholds. Dose increase back to 12 mg BID (or 30 mg QD from January 2017) is not allowed.

From January 2017, all subjects who are at Week 72 or beyond will receive a once-daily tablet formulation. Subjects who are on 6 mg BID capsule dosing will be transitioned to 15 mg QD tablet dosing. Subjects who are on 12 mg BID capsule dosing will be transitioned to 30 mg QD tablet dosing. The capsule formulation will not be available to subjects once the transition to tablet formulation has occurred.

[figure not shown]
Starting with Amendment 5, subjects who are receiving 30 mg QD open-label upadacitinib will have the option to decrease the dose to 15 mg QD based on investigator's discretion.

The change to once daily tablet formulation in this study is based on extrapolation of pre-clinical efficacy models and analyses of PK, pharmacodynamic, safety, and efficacy data from the Phase 1 studies in healthy volunteers (single and multiple ascending dose Studies M13-401 and M13-845, respectively) and completed Phase 2b randomized, controlled studies (RCTs) in RA subjects (Studies M13-537 and M13-550). The doses

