### **Clinical Laboratory Tests**

Samples will be obtained at minimum for the clinical laboratory tests outlined in [Table 3](#). A certified central laboratory will be utilized to process and provide results for the clinical

laboratory tests. All abnormal laboratory tests that are considered clinically significant by the investigator will be followed to a satisfactory resolution.

The central laboratory chosen for this study will provide instructions regarding the collection, processing and shipping of these samples.

The fasting status will be recorded in the study source documentation.

If travel restrictions or other changes in local regulations due to state of emergency or pandemic situation like COVID-19 prevent the subject from having blood drawn for laboratory testing at the study site, it is possible for the Investigator to arrange for subjects to have laboratory work done at a local lab, hospital, or other facility to ensure the safety assessments are conducted per protocol. Local lab results should be obtained along with reference ranges and kept within the subjects' source documentation. Local lab results should be reviewed by the investigator or designee as soon as possible and documented in the eCRF.

If laboratory samples cannot be obtained, study drug administration may be continued provided labs have been obtained within the prior 3 months, the investigator has reviewed the laboratory results and confirmed and discussed with the subject that there is no safety concern for the subject to continue use of the study drug in the absence of current lab results. The subject should be scheduled for laboratory draws as soon as feasible and no later than the next scheduled visit in order to continue the study drug administration.

If laboratory results are not available within the prior 3 months/two consecutive 12-week intervals, study drug dispensation is not allowed until the required laboratory tests are completed to ensure the safety assessments are conducted per protocol.

Blood and samples will be obtained for the laboratory tests as specified in [Table 2](#). Blood draws should be performed after all clinical assessments and questionnaires (HAQ-DI, Patient's Assessment of Pain, FACIT, etc.), and vital sign determinations are obtained and before study drug administration during a visit.

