9.0 Efficacy Analysis

9.1 General Considerations

Long-term efficacy analysis will be performed on the Open-Label Treated Population by the treatment group sequences as defined below:

1. Upadacitinib never titrated (6 mg BID/15 mg QD),
2. Upadacitinib titrated up and not down (6 mg BID/15 mg QD to 12 mg BID/30 mg QD), and
3. Upadacitinib titrated up and down (6 mg BID/15 mg QD to 12 mg BID/30 mg QD and then back down to 6 mg BID/15 mg QD).

No statistical tests will be conducted; only descriptive statistics and confidence intervals will be provided. All data will be summarized based on As Observed data (defined in Section 9.1.1).

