10.3.2 Assessment of Mean Change from Baseline in Clinical Laboratory Values

Analyses of mean change from baseline in continuous hematology, chemistry, and urinalysis variables which are measured longitudinally will be performed by visits and by treatment group. For each change from baseline analysis, the following summary statistics will be presented for each treatment group sequence: sample size, baseline mean, visit mean, and the mean, standard deviation, and median of the changes from baseline.

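### Mean laboratory and vital-sign changes and laboratory shifts are grouped only by eventual titration sequence, so they do not show change by the dose being taken when the sample was drawn

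*SAP*

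**What the plan says.** The main-study SAP uses two grouping schemes for safety data.

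- **Sequences (SAP 9.1).** There are three whole-course labels: never titrated, up and not down, and up then down. The second reads "Upadacitinib titrated up and not down (6 mg BID/15 mg QD to 12 mg BID/30 mg QD", so it covers both dose periods of the same subject. SAP 10.1 applies the sequences to mean changes: "Mean changes from baseline in all continuous laboratory parameters and vital signs variables at each visit will be summarized by the treatment group sequences". SAP 10.3.2 repeats this for laboratory values: "the following summary statistics will be presented for each treatment group sequence: sample size, baseline mean, visit mean". SAP 10.4.2 names no other grouping for vital signs. SAP 10.3.3 puts the shift tables by sequence too, with some latitude as to which tables are appropriate.
- **Exposure groups (SAP 8.1).** Lower-dose time is cut off at the increase, higher-dose time at any later reduction, and time after a reduction is a third group. A fourth group is any upadacitinib. These groups are used for adverse event rates (SAP 10.2), events of special interest (10.2.5) and liver elevations (10.3.5). SAP 10.1 also uses them for out-of-range values: tables and listings for "potentially clinically significant laboratory values will be provided by the exposure groups defined in Section 8.1", and likewise for vital signs.

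On dosing, Protocol 5.1 says "All eligible subjects will be assigned to upadacitinib 6 mg BID", and later "Starting at Week 6 and during any scheduled or unscheduled visits thereafter, upadacitinib dose may be increased from 6 mg BID to 12 mg BID". It allows a reduction at any visit for an adverse event or on reaching a toxicity threshold, and from Amendment 5 a reduction from 30 mg QD at the investigator's discretion. Protocol 5.3.1.1 has blood drawn "before study drug administration during a visit", and vital signs taken before the blood draw.

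**The concern.** A sample's column is fixed by what happens to the subject over the whole study, including after the sample is taken. A lower-dose sample goes to sequence 1 if the dose is never raised and to sequence 2 or 3 if it is raised later. A higher-dose sample goes to sequence 2 or 3 depending on whether the dose is later reduced. No column of mean changes or shifts corresponds to being on 12 mg BID/30 mg QD.

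Long-term safety is part of the primary objective, and SAP 10.1 lists mean change among the long-term safety analyses. Clinically significant laboratory values are defined in SAP 10.3.4 as Grade 3 or 4. Under Protocol 6.3.1 a laboratory abnormality is an adverse event only in limited circumstances. Changes below Grade 3 therefore appear mainly in the mean-change and shift tables, the ones not organised by dose taken. Protocol 8.1.6.1 gives mean changes by visit with no dose split, and Protocol 8.1.7 makes the exposure-safety analysis optional.

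**Working it through.** The plan states no figure on this point, so there is none to reproduce. The check follows from the dosing rules and the visit windows.

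**1. Week 6.** All subjects start on 6 mg BID, the first increase is possible at the Week 6 visit, and vital signs and blood come before dosing. Every scheduled Week 6 sample is therefore on the lower dose, in every sequence. One narrow exception exists. SAP Table 1 gives Week 6 a window of days 2 to 64 with target day 43. SAP 5.3 takes the visit closest to target, the later one on ties. Scheduled visits may fall 7 days either side (days 36 to 50). An unscheduled sample after an increase can replace the scheduled one only if it is at least as close to day 43:

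- visit on day 36: replacement possible on days 37 to 50
- visit on day 42: replacement possible on days 43 to 44
- visit on days 43 to 50: none possible

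**2. Later visits.** SAP Table 1 has 27 post-baseline visits (Weeks 6 and 12, then 25 visits from Week 24 to Week 312). A subject increased at the Week 48 visit supplies 5 of the 27 (Weeks 6, 12, 24, 36, 48) on the lower dose. One increased at Week 96 supplies 9 of 27. All are counted in sequence 2.

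**3. What the column shows.** At a given visit let f be the share of sequence 2 samples on the higher dose, mL and mH the mean changes in its lower-dose and higher-dose samples, and m1 the mean change in sequence 1. Then

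sequence 2 mean = (1 − f) × mL + f × mH

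sequence 2 − sequence 1 = (mL − m1) + f × (mH − mL)

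The first line is arithmetic and needs no assumption. In the second, mL − m1 compares people later increased with people never increased, both on the lower dose. Its sign is unknown. At scheduled Week 6 samples f = 0 and only this term remains. Nor is mH − mL a pure dose effect, because the subjects already increased are not a random part of the column.

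**4. Range of f.** The documents give no distribution of titration times. As an assumption only, take exponential times after Week 6 among those eventually increased, median M weeks, no dropout: f = 1 − 0.5^((week − 6)/M). For example, at Week 24 with M = 12, f = 1 − 0.5^(18/12) = 0.65.

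| Week | 6 | 12 | 24 | 48 | 96 | 192 | 312 |
|---|---|---|---|---|---|---|---|
| M = 12 | 0 | 0.29 | 0.65 | 0.91 | 0.99 | 1.00 | 1.00 |
| M = 48 | 0 | 0.08 | 0.23 | 0.45 | 0.73 | 0.93 | 0.99 |

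Mixing is largely over by Week 48 in the first row and still material at Week 96 in the second. The plan does not say which is closer.

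**5. Subjects later reduced.** A subject reduced after reaching a toxicity threshold has every sample, including those on the higher dose, placed in sequence 3. Protocol Table 5 sets such thresholds for hemoglobin, cell counts, transaminases, creatinine and CPK. Sequence 2 thus loses the higher-dose samples of these subjects, and sequence 3 pools three dose periods.

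**6. Lining up outputs.** The lower-dose exposure group includes time before an increase in subjects later increased; sequence 1 leaves those subjects out. The higher-dose exposure group includes time from subjects later reduced; sequence 2 leaves them out. Neither pair describes the same samples.

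**7. With samples grouped by dose at sampling.** f = 1 in the higher-dose group at every visit, so the mixing is gone. That group has no regular Week 6 samples.

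**The case against.** The strongest reply is that dose-specific laboratory safety is already largely covered. Grade 3 or 4 values, liver elevations and the special-interest categories for anemia, neutropenia, lymphopenia, CPK, renal and hepatic events are all by exposure group. The Grade 3 and 4 hemoglobin criteria include a fall from pre-treatment, and whole-course listings are given for subjects with such values. This stands, and it limits the point to mean changes and shift tables.

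The choice is also recorded: the SAP's change log for version 3.0 says laboratory analyses go by sequence. The labels name both doses, the tables carry no tests, and stable membership is a fair way to show long-term means. By-visit exposure groups have their own weakness. The lower-dose group becomes enriched for responders, and the higher-dose group collects inadequate responders with differing time on dose. These arguments stand as reasons to keep the sequence tables. They are not reasons against adding on-dose tables beside them.

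A reader might infer that the higher dose's effect is understated at Week 6, or diluted at each visit by exactly the share not yet increased. The documents do not support either reading. At scheduled Week 6 samples nobody is on the higher dose, so there is no effect to understate. Proportional dilution of the contrast with sequence 1 would need sequences that are otherwise comparable. Increases follow less than 20% improvement in joint counts or a CDAI above 10, so the sequences are not comparable.

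**Conclusion.** The point holds for by-visit mean laboratory and vital-sign changes and for laboratory shift tables. Where titration is incomplete, sequence 2 pools doses. Higher-dose samples from subjects later reduced sit elsewhere, and a worst or final shift category can come from either dose period. These outputs cannot be read by dose taken or matched to the exposure-group outputs.

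The size is not computable from the documents. It is greatest at early visits and shrinks as the share increased approaches 1. Required increases at Weeks 6 and 12 may confine much of it to early visits, but the CDAI rule permits increases throughout. The direction of any net bias is uncertain. This is a gap in presentation that is worth closing. It does not invalidate the safety analysis.

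**What to change.** Keep the sequence tables in SAP 10.3.2, 10.3.3 and 10.4.2. Add by-visit mean-change tables (laboratory and vital signs) and laboratory shift tables by dose at the time of the sample, using the four exposure groups of SAP 8.1. State that:

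- a sample taken at the visit where the dose changes belongs to the dose taken before the change;
- final, minimum and maximum shift categories are taken from samples within that group's exposure;
- baseline remains the RCT baseline of SAP 5.2.

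Add a footnote that group membership changes across visits and that confounding by the reason for titration remains, so differences between columns are not estimates of a dose effect.

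The cost is SAP wording, programming and extra tables. The grouping is already needed for the adverse event and clinically significant value outputs. No change to data collection, dosing rules or the protocol is required.
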